UNIVERSIDADE DA CORUÑA

Grupo de Investigación en Gerontología y Geriatría

Study Protocol and Statistical Analysis Plan

Protocol Official Title: **Low-volume Cycling Training Improves Body Composition and Functionality in Older People With Multimorbidity: a randomized controlled trial**

ClinicalTrials.gov ID: [Not yet assigned]

Date: 6th April 2021

Grupo de Investigación en Gerontología y Geriatría ©
Universidad de A Coruña

INTRODUCTION

Aging is a risk factor for most chronic diseases, and the presence of more than two diseases (i.e., multimorbidity), which is frequent in almost two out of three older adults, has been related to an increased risk of disability and frailty, a decrease in quality of life, and mortality (Pedersen, 2019). Physical activity (PA) acts as a nonpharmacological intervention and regular physical activity (rPA) reduces rates of all-cause mortality, compresses morbidity, decreases healthcare costs, and has relatively minimal adverse effects compared to drugs (Fiuza-Luces et al., 2013).

It has been estimated that 27.5% of the world's population in 2016 did not meet the recommendations established for the member states of the World Health Organization (WHO) for health-enhancing physical activity. Furthermore, recent studies showed that moderate-intensity physical activity may be sufficient for reducing the risk of all-cause dementia and that some of the protective benefits of physical activity for older adults (Cunningham et al., 2020). It seems indispensable to study adequate doses of exercise for older people who often have low levels of physical activity and fitness, who spend a large amount of time sitting down, and whose multimorbidity keeps them away from exercising.

OBJECTIVES

To study the effects of perception-regulated low-volume and low-to moderate intensity training on body composition, hemodynamic parameters, and functional performance in older adults with multimorbidity.

MATERIAL AND METHODS

Study design

This longitudinal and prospective study conducted between September and December 2019, is a 2 x 2 randomized controlled trial using a two-group design (exercise vs. control) and two repeated measures (pre- vs. postintervention). This study is performed following the CONSORT (CONsolidated Standards of Reporting Trials) 2010 guideline.

Study setting and participants

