Participants are recruited between September and October 2019 at the Gerontological Complex La Milagrosa (A Coruña, Spain), consisting of a daycare center and a nursing home.

Inclusion criteria: (a) men and women aged 65 and older, (b) users of a care setting—daycare patients or nursing home residents, and (c) a score < 5 in the Global Deterioration Scale (GDS; Reisberg et al., 1982), from no cognitive decline to moderate cognitive decline.

Exclusion criteria: (a) physical limitations or musculoskeletal injuries that could affect cycling training performance; physical exercise contraindicated by the physiotherapist and verified by the medical doctor according to the medical register of each participant; (b) heart failure with a functional class according to the New York Heart Association (NYHA) Classification of NYHA III and IV; (c) the presence of acute pain that does not allow exercise training; (d) recent acute

myocardial infarction (in last 6 months) or unstable angina; (e) uncontrolled hypotension; (f) uncontrolled arterial hypertension ($>180/100$ mmHg); (g) active cancer treatment with chemotherapy; (h) patients with an active pacemaker and/or uncontrolled block; (i) diabetes mellitus with acute decompensation or uncontrolled hypoglycemia; or (j) any other circumstance that precludes individuals from completing the training intervention.

24 participants will be recruited and randomly placed into two groups: the exercise group (EG, n=12) and the control group (CG, n=12). A stratified permuted block randomization is employed that accounted for the GDS score, sex, and type of institutionalization. A nurse and a medical doctor enrolled and assigned participants to intervention.

Intervention

Cycloergometers

The Gerontological Complex La Milagrosa features a kinesiotherapy room equipped with three MOTOMed®muvi cycle ergometers (Fig. 1) adapted for older people. These cycle ergometers have the ability, through electric motors, to provide resistance to oppose cycling and, on the other hand, to passively move the limbs of the trainees. This movement system allows even subjects with loss of functional ability to mobilize (bipedestation or walking) to perform the activity from their wheelchair or geriatric chair.

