Pre- and post-intervention assessments are made on all subjects of the sample (control and experimental group). Pre-intervention data were collected one week before the start of training, while post-intervention data were recorded at the end, after six weeks of intervention.

Socio-demographic variables

Age (years) and gender.

Body composition evaluation

Bioimpedance analysis (Inbody 270): body weight (kg), height (cm), muscle mass (MM), fat mass (FM), and FM percentage. Waist circumference (WC, cm) is taken at end-tidal using a measuring tape to the nearest 0.1 cm, midway between the lowest rib and the iliac crest, which corresponded with the level of the umbilicus. Body mass index (BMI) is established by the Quetelet index: $BMI \text{ (kg/m}^2\text{)} = \text{mass (kg)} / \text{height (m)}^2$.

Figure 3. InBody 270

Hemodynamic parameter evaluation

The baseline hemodynamic state is characterized by storing the mean of the three lowest values for thirty seconds of heart rate (HRrest, mm Hg) and oxygen saturation with a finger pulse oximeter; blood pressure by the auscultator method using a properly calibrated mercury column sphygmomanometer flexible cuff of the appropriate size and a stethoscope; three systolic (SBPrest) and diastolic blood pressure (DBPrest) measurements are recorded at 1-minute intervals. Mean blood pressure (MBPrest) is calculated as follows:

$$\text{MBP} = \text{DBP} + 1/3 (\text{SBP} - \text{DBP}).$$

Functional evaluation

- a) Frailty. Assessed by Fried et al. (2001), based on the presence or absence of 5 specific and phenotypic components (1) unintentional weight loss: at least 4.5 kg in the past year; (2) self-reported exhaustion, identified by 2 questions from the modified 10-item Center for Epidemiological Studies-Depression scale; (3) weakness: grip strength in the lowest 20% at baseline, adjusted for sex and body mass index; (4) slow walking speed: the slowest 20% at baseline, based on time to walk 4.6 m, adjusting for sex and standing height; and (5) low physical activity: the lowest 20% at baseline, based on a weighted score of kilocalories expended per week.
- b) The Performance-Oriented Mobility Assessment (i.e., POMA; Tinetti, 1986), which measures balance (i.e., POMA-B) and gait performance (i.e., POMA-G) and the total score (i.e., POMA-T).

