Data will be presented as the median and interquartile range for ordinal variables and the estimated marginal mean \pm standard deviation (SD) for continuous variables. The effect of the intervention will be analyzed employing nparLD (robust rank-based analysis of longitudinal data in factorial experiments) from the RStudio software package for nonparametric variables. Changes within and between groups will be analyzed by employing mixed models for repeated measures designs with the module GAMLj, which uses the R formulation of random effects as implemented by the lme4 R package in Jamovi software. The mixed models are a modern class of statistical models that extend regular regression models by including random effects parameters to account for dependencies among related data. We have chosen mixed models analysis as we expect a within-subject dependency in the variables measured before and after the intervention. Compared to traditional analyses that ignore these dependencies, mixed models provide more accurate (and generalizable) estimates of the effects, improved statistical power, and non-inflated Type I errors.

Duration of the project

	2019					2020	2021
	Jan-Aug	Sept	Oct	Nov	Dec	Jan-Dec	Jan-Dec
1. Project preparation and methodology							
2. Recruitment							
3. Baseline assessment							
4. Intervention (6 weeks per user)							
5. Post-intervention assessment							
6. Data analysis							
7. Dissemination							

References

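### The mixed model for continuous outcomes, as naturally read, is a change-score comparison: valid, but not adjusted for baseline

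*SAP*

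**What the plan says.** The Study design section describes a 2 × 2 trial "using a two-group design (exercise vs. control) and two repeated measures (pre- vs. postintervention"). Under Study setting and participants the sizes are "the exercise group (EG, n=12) and the control group (CG, n=12"), with randomization stratified on GDS score, sex and type of institutionalization. Under Measures, "Pre- and post-intervention assessments are made on all subjects of the sample (control and experimental group").

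Data management and statistical analysis then says: "Changes within and between groups will be analyzed by employing mixed models for repeated measures designs with the module GAMLj", using random effects as implemented in lme4. Its stated reason is the expected dependency between a participant's values before and after the intervention. It adds: "Compared to traditional analyses that ignore these dependencies, mixed models provide more accurate (and generalizable) estimates of the effects, improved statistical power".

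No fixed-effects formula, baseline covariate or constraint of equal baseline means is given. Variables called nonparametric go to nparLD and are outside this point.

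**The concern.** With two time points and the pre value treated as a response, the obvious lme4 model is group, time, group × time and a random intercept per participant. Its group × time term compares mean changes between arms.

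A change score subtracts the whole baseline value, which is right only if the slope of post on baseline is 1. If the slope is lower, an arm that happens to start high is expected to fall back, and the change score counts that as effect. In a trial this small, sizeable chance imbalance on some outcome is likely. For that outcome the estimate is off-centre. For outcomes of moderate stability the variance is also larger than it need be.

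The SAP's argument about power does not meet this point. It compares mixed models with analyses that ignore within-subject dependency. A change-score t-test does not ignore it, and on complete data the mixed model gives the same answer as that test.

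**Working it through.** **Inputs.** From the SAP: 12 per arm and two measurements per participant. Assumed, because the SAP gives no values: pre-post correlation ρ, the SD ratio k = SDpost/SDpre (1 unless stated), and a two-sided 5% level with 95% CI as yardstick. The SAP has no figure of its own to reproduce.

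**1. Equivalence.** In one simulated complete data set with 12 per arm, the random-intercept REML fit gave group × time = −0.1962 (SE 0.3350). The difference in mean change was −0.1962 (SE 0.3350). The mixed model therefore adds no power over the change-score test.

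**2. Validity.** In 40,000 simulated null trials per setting, change-score type I error was 5.1, 5.1, 5.0 and 4.9% at ρ = 0.5, 0.7, 0.9 and 0.95. Averaged over randomization there is no bias.

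**3. Size of chance imbalance.** The SD of the baseline difference is √(2/12) = 0.41 outcome SD. If sex, a stratification factor, explained 25% or 50% of an outcome's variance (assumed), this falls to 0.37–0.39 or 0.33–0.37.

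**4. Shift given an imbalance.** The change score carries over −(1 − ρk) times the baseline difference. At 0.41 SD and ρ = 0.5 this is 0.5 × 0.41 = 0.20 SD.

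**5. Variance over randomization.**
- Change score: (1 + k² − 2ρk) × 2/12, 22 df.
- Baseline-adjusted: k²(1 − ρ²) × 2/12 × (1 + 1/20), 21 df.
- At ρ = 0.5, k = 1: 0.1667 against 0.75 × 0.1667 × 1.05 = 0.1313, ratio 1.27.
- Break-even at k = 1: 2/1.05 − 1 = 0.905.

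| ρ (k = 1) | Shift at 0.41 SD | Variance ratio, change/adjusted | Adjusted power where change score has 60% |
|---|---|---|---|
| 0.5 | 0.20 | 1.27 | 70% |
| 0.7 | 0.12 | 1.12 | 65% |
| 0.8 | 0.08 | 1.06 | 62% |
| 0.9 | 0.04 | 1.00 | 60% |
| 0.95 | 0.02 | 0.98 | 59% |
| 0.98 | 0.01 | 0.96 | 58% |

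**6. Coverage of the change-score 95% CI with the baseline difference held fixed** (100,000 simulated null trials per setting, k = 1):

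| Baseline difference | ρ = 0.5 | 0.7 | 0.8 | 0.9 |
|---|---|---|---|---|
| 0 | 97.4% | 96.6% | 96.0% | 95.6% |
| 0.41 SD (1 SE), error in each tail | 0.3/4.7% | 0.6/4.4% | 0.9/4.1% | 1.2/3.8% |
| 0.82 SD (2 SE, about 1 outcome in 20) | 87.3% | 90.3% | 91.8% | 93.5% |

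At 0.41 SD total coverage is about 95%, but the errors are lopsided. The adjusted interval covers 94.9–95.1% throughout. At 0.82 SD it is not always narrower: mean half-widths, change score against adjusted, are 0.84 v 0.80, 0.65 v 0.66, 0.53 v 0.55 and 0.38 v 0.40.

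**7. Unequal SDs**, at ρ = 0.5, 0.7, 0.8, 0.9:
- k = 0.8: carry-over 0.60, 0.44, 0.36, 0.28; variance ratio 1.67, 1.52, 1.49, 1.57. Coverage at 0.82 SD is 81.6–84.0%, so high ρ alone does not protect the change score.
- k = 1.25: carry-over 0.38, 0.13, 0.00, −0.13; variance ratio 1.07, 0.97, 0.95, 1.00. Coverage at 0.82 SD is 91.7, 94.4, 95.0, 93.3%.

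**The case against.** **The model is inferred.** This stands. The SAP names a class of model and not a formula, and a model with a common baseline mean would remove the problem. Even so, nothing in the text points to such a model.

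**The planned test is valid and the SAP's power sentence is not false.** Both stand. The sentence compares only with analyses that ignore dependency. The issue is efficiency and behaviour given an imbalance, not type I error over randomization.

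**The gain depends on unknown quantities and may be nil.** This stands in part. Six of about 12 continuous outcomes are body-composition measures, which may have ρ of 0.9 or more over six weeks. The five hemodynamic measures are not independent, since mean pressure is computed from the other two. Some skewed measures may go to nparLD. Repeated readings also tend to raise ρ: heart rate and saturation are averages of three values, and "three systolic (SBPrest) and diastolic blood pressure (DBPrest) measurements are recorded at 1-minute intervals". Readings taken at one sitting do not remove variation between visits, however.

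**The 5% cost is an average, while the coverage loss is conditional on imbalance.** This is fair. At z standard errors of imbalance the adjusted estimator's variance is 1 + z²/20 times the change score's, so 1 + 4/20 = 1.20 at 2 SE. But the change score then also carries its shift. With k = 1 the ratio of mean squared errors is [1 + z²(1 − ρ)/(1 + ρ)] / (1 + z²/20). At z = 2 this gives 1.94, 1.42, 1.20 and 1.01 for ρ = 0.5, 0.7, 0.8 and 0.9. Adjustment is not worse anywhere in that range.

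**Regression on baseline drops anyone missing a value.** This has little force, because the SAP has both assessments made on all participants.

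**The change may be post hoc.** This stands. The document is dated April 2021, the design section reads "This longitudinal and prospective study conducted between September and December 2019", and the title already claims improvement. It bears on how the change is reported.

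**Conclusion.** The point holds as an improvement that should be made, with medium confidence. As naturally read, the planned between-group estimate is a change-score difference: valid over randomization, off-centre when baselines differ and the post-on-baseline slope is not 1, and less precise at moderate correlation.

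With equal SDs the variance penalty is 27% at ρ = 0.5, 6% at 0.8 and nil near 0.9. Beyond 0.905 the change score is slightly better. Hemodynamic measures and chair sit-and-reach are the likeliest to gain; body composition may gain nothing.

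This rests on the inferred formula, complete data and assumed values of ρ and the SD ratio.

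**What to change.** For each continuous outcome, take the between-group estimate from post value ~ group + baseline value, and report the adjusted difference with its 95% CI. Keep the mixed model to describe within-group change. Adjustment for the stratification factors is optional and not part of this change. If a model with a common baseline mean or a baseline covariate was intended all along, writing out its formula settles the point.

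The cost is one formula in the planned software, using values already collected. It uses 1 of 22 degrees of freedom. Averaged over randomization it costs at most 5% of variance, reached when the post-on-baseline slope is 1 (2–4% at ρ = 0.95–0.98 with equal SDs).

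Date the change. If outcomes have already been examined, report the planned group × time contrast beside the adjusted one.

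### Allocation is stratified on GDS score, sex and type of institutionalization, but the mixed-model description does not include them; the treatment contrast loses precision to the extent that they predict change

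*SAP*

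**What the plan says.** On allocation, SAP, Study setting and participants: "A stratified permuted block randomization is employed that accounted for the GDS score, sex, and type of institutionalization". The trial has 24 participants, 12 per group. Eligibility requires "a score < 5 in the Global Deterioration Scale", and participants are "users of a care setting—daycare patients or nursing home residents", so setting has two levels. Neither the GDS grouping used for stratification nor the block size is given.

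On analysis, SAP, Data management and statistical analysis: "Changes within and between groups will be analyzed by employing mixed models for repeated measures designs with the module GAMLj". The stated reason for the model is within-subject dependence: "We have chosen mixed models analysis as we expect a within-subject dependency in the variables measured before and after the intervention". Nonparametric variables go to a rank-based longitudinal analysis (nparLD). No stratification factor or other covariate is named for either method, no list of fixed effects is written out, and the treatment contrast is not named. Since the pre and post values are both responses, the natural reading is the group-by-time term, that is, the between-group difference in change.

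**The concern.** When randomisation is balanced within strata, the true sampling variance of the treatment contrast falls by the part of the outcome that the strata explain. A model that omits the strata leaves that part in the residual, so it reports a standard error for a less precise design than the one run. Intervals are then too wide and the test rejects too rarely.

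A second effect runs alongside. With few participants per stratum many blocks stay incomplete, so some imbalance in the factors remains, and an unadjusted model does not correct for it. With 12 per group there is little precision to spare.

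**Working it through.** **1. Inputs.** From the SAP: N = 24, 12 per group, two time points, three stratification factors, two settings. Assumed, because the SAP gives none: two-sided 5% test, complete data, GDS scores 1 to 4 each forming a level, block size 2 or 4, an effect of 1.2 SD of the change score, and R², the share of the variance of change that the factors explain. There is no sample-size calculation in the document to reproduce.

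**2. Strata.** 4 × 2 × 2 = 16 strata, and 24 / 16 = 1.5 participants per stratum. With GDS in two levels it would be 8 strata and 3 per stratum. With blocks of 4, the simulated exercise group missed 12 by 1.0 (two GDS levels) to 1.4 (four levels) participants on average, so residual imbalance is plausible.

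**3. What cancels.** With complete pre/post data and a participant random intercept, the group-by-time estimate is the difference in mean change. Anything constant within a participant that shifts both values equally drops out. In one simulated trial the random-intercept model gave:

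| Fixed effects | Group-by-time estimate | SE |
|---|---|---|
| group × time | 0.25996 | 0.34332 |
| plus factors as main effects | 0.25996 | 0.34332 |
| plus factors crossed with time | 0.18972 | 0.38482 |

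Main effects alone therefore do nothing for this contrast; the factors must be crossed with time. In that trial they did not predict change, and crossing them raised the SE.

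**4. Size when the factors predict change.** In units of the SD of change, the unadjusted SE is about √(2/12) = 0.41. If balance were perfect, the true SD of the estimate would be 0.41 × √(1 − R²); at R² = 0.3 that is 0.41 × 0.837 = 0.34. Incomplete blocks reduce the gain. Simulation with 16 strata compared change on group (22 df) with change on group, sex, setting and linear GDS (22 − 3 = 19 df). Ranges cover both block sizes and repeated runs:

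| Assumed R² | Unadjusted: SE / true SD | Type I error, without / with factors | Power, without / with factors |
|---|---|---|---|
| 0 | 0.41 / 0.40-0.42 | SE correct | about 79% / 76%; loss 3-4 points in most runs |
| 0.1 | – | – | about equal |
| 0.2 | – | 3.4-3.9% / 4.4-5.8% | 80-81% / 84-86% |
| 0.3 | 0.41 / 0.36-0.39 | 2.6-3.9% / 4.9-5.5% | 80-82% / 88-90% |

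At R² = 0.3 the reported SE is too large by 0.41/0.39 = 1.05 to 0.41/0.36 = 1.14, or 5 to 14%.

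A separate simulation (pre/post correlation 0.7, factor coefficient 0.3 on change) fits this pattern. There the variance of change is 2 × 0.3 + 0.09 = 0.69, so R² is about 0.09/0.69 = 0.13. Adjustment lowered the SE from 0.344 to 0.333 (four GDS levels) or from 0.343 to 0.326 (two levels), a fall of 3 to 5%. Where the factors predicted level only, unadjusted type I error for change was 0.044-0.050, and adjustment raised the SE slightly (0.319 to 0.327, or 0.320 to 0.335).

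**5. If a group difference at post is reported.** Here level effects do matter. With the factors explaining 0.1, 0.3 and 0.5 of outcome variance, unadjusted type I error was 0.042, 0.029 and 0.016 (two GDS levels), or 0.040, 0.034 and 0.027 (four levels).

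**The case against.** The strongest objection is that nothing in the document shows that sex, setting or GDS score predicts six-week change. Without that, the group-by-time standard error is correct and adjustment only spends degrees of freedom. This stands. A reader might infer that the planned contrast necessarily has too large a standard error; the document does not support that, and the point is conditional.

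Three other inferences also go too far.

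- A reader might say that the plan excludes the factors from the model. It writes no fixed-effect list at all, so one can say only that the description does not include them.
- A reader might see a contradiction with the claim of "improved statistical power, and non-inflated Type I errors". That sentence compares mixed models with analyses that ignore within-subject dependence. It makes no claim about stratification factors, so there is no conflict.
- A reader might argue that an imbalance in sex would distort the result for muscle or fat mass because men and women differ on them. That is a difference in level, and it cancels from group by time.

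It is also fair to say that the error is in the conservative direction: false positives are not inflated. What survives is that the design restricts allocation on three factors and the analysis does not say how they are used, although the remedy is cheap and the possible gain exceeds the possible loss.

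**Conclusion.** The point holds in conditional form. The analysis description is not aligned with the stratified allocation. For the difference in change, this costs precision only as far as the factors predict change. At an assumed R² of 0.3, power is about 80% where 88-90% was available and type I error is about 3-4%; at 0.1 there is no material difference; at 0 the unadjusted model is better by about 3-4 points of power. If a group difference at post is reported, factors that predict level alone are enough to make the test conservative.

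These figures rest on the assumed effect, strata, block sizes and R², none of which the SAP gives. The change is worth making because it costs little, not because a loss has been shown.

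**What to change.** In Data management and statistical analysis, state that the model for each continuous outcome contains group, time and group by time, together with sex, type of institutionalization and GDS score (linear, or as categorised for randomisation), each crossed with time, and a participant random intercept. Name group by time as the treatment contrast. Report the model without the factors as a sensitivity analysis. Do not use one indicator per stratum: 16 strata would take too many of the 22 degrees of freedom.

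A model for the post value is an alternative only if it also includes the outcome's baseline value, and it is not equivalent to the model above. Without baseline it does badly: at an assumed pre/post correlation of about 0.8, power was 36-50% across two sets of runs.

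The cost is one sentence and three residual degrees of freedom (22 to 19) with GDS linear or in two groups. With GDS in four categories it is 1 + 1 + 3 = 5 (22 to 17). If the factors predict nothing, about 3-4 points of power are lost. The factors were needed for randomisation, so no new data are required. The change does not cover the rank-based analysis, for which the plan should say separately whether the factors are used.
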